1.0 Background

Video-assisted thoracic surgery (VATS) is being performed more frequently due to its less invasive nature, decreased postoperative pain, and shortened post-operative hospital stay. However, VATS procedure still results in significant postoperative pain and the ideal analgesic for postoperative pain control following VATS remains unclear. Many modalities for pain control have been addressed in the literature: NSAIDs, opioids, epidurals, paravertebral blocks, and surgeon infiltration (1, 2). These have been used to manage the significant postoperative pain from VATS procedures remains to be codified and changes based on provider preference. The purpose of this study is to determine the effectiveness of Erector Spinae Plane Block (ESP) versus surgeon infiltration for postoperative analgesic control after VATS.

Erector Spinae Plane block was first described by Forero in 2016. This block has shown promise in relieving neuropathic pain and in providing analgesic coverage in laparoscopic cholecystectomy, mastectomy, and thoracic surgeries (3-7). This block can be thought of as a modified paravertebral block, and shows promise of increased safety compared to the paravertebral block. This is due to the unique anatomical approach that allows for anesthetic infiltration of the dorsal rami without the risk of needle insertion into the paravertebral space (6). The improved safety of this approach could allow this block to be used on higher risk patients, like those who present with coagulopathies.

Another common method of managing postoperative VATS pain is through surgeon infiltration of the intercostal space with local anesthetic. To perform infiltration, surgeons inject the anesthetic with direct visualization of the intercostal space, providing targeted analgesic coverage to the affected area (8). Some drawbacks to this process are the relatively short duration of action of the block, and the requirement of the surgeon to inject all affected intercostal spaces to achieve the desired dermatomal block(1, 2).

Exparel®, a liposomal formulation of bupivacaine (LB), has shown significant promise in providing extended analgesic coverage in the postoperative period. Due to its extended release format, LB can provide analgesia coverage for up to 72 hours postoperatively when compared to normal saline and has been suggested to reduce postoperative opioid use as well (9). It has provided effective analgesia in total knee arthroplasty and hip arthroplasty and has shown promise in open and laparoscopic colectomy (10-12). However, there are also studies showing that LB might not be superior to standard bupivacaine (SB) in terms of duration of analgesia (13-15). In order to compare the duration of action of both form of bupivacaine, we'll randomized the ESP group to both LB group and SB group.

Our hypothesis is that ESP block is superior to surgeon infiltration for pain scores, and LB will be superior to SB for ESP block duration of action.

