5.0 Study Procedures

All the erector spinae plane blocks will be placed preoperatively after sedation, before intubation and prior to surgery. All procedures will be done using sterile technique with masks, hats, and sterile gloves. All procedures will be placed under the supervision of the attending anesthesiologist on the acute pain service or the attending anesthesiologist in the VATS room.

To perform the ESP block, an ultrasound probe is used to visualize the ES musculature about 3 cm laterally from the T5 spinous process. In a cephalad-to-caudad direction advance the needle and inject the anesthetic in the interfacial plane deep to the ES muscles. Confirm positioning by visualization of needle tip and elevation of ES muscles off the transverse process with anesthetic injection. Surgeon infiltration is performed intraoperatively under direct thoracoscopic guidance. The intercostal space will be visualized and injected with LB. Typically, T4 through T8 are infiltrated with 2-3mL of the anesthetic mixture.

All patients will receive 1gm of acetaminophen and 600mg of gabapentin preoperatively. Patients above 70yo will receive 300mg of gabapentin. General anesthesia will be induced in the operating room and the patient will be placed in the lateral position for the VATS procedure. All patients will

receive intraoperative lidocaine and ketamine which is used to decrease opioid use after surgery and is being used as part of ERAS protocol. The patients will be intubated with dual lumen endotracheal tubes and placed on one-lung ventilation for the procedure. All patients will receive intravenous patient-controlled analgesia (PCA hydromorphone) post-operatively for breakthrough pain. They will also be scheduled on PO acetaminophen. PO oxycodone PRN will be started on POD 1 once patients tolerate diet.

Opioid usage at 1,24,48,72 hours after the block will be recorded by a member of the research team. Pain scores at rest and on movement (knee flexion) will be measured by the investigator using Visual Analog Scale (VAS). Nausea will be measured using a categorical scoring system (none=0; mild=1; moderate=2; severe=3). Sedation scores will also be assessed by a member of the study team using a sedation scale (awake and alert=0; quietly awake=1; asleep but easily roused=2; deep sleep=3). All these parameters will be measured at 1, 24, 48 and 72 hours after the epidural or PVB. Patients will be encouraged to ambulate on postoperative day 1 under supervision.

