8.0 Statistical Considerations

Primary outcome: VAS score at 24 and 48 hours

Primary Research Hypothesis: ESP will provide lower pain scores compared to surgeon infiltration and ESP with LB will provide longer pain control than ESP with SB.

Secondary outcomes: Opioid usage after 1, 24, 48 and 72 hours. Pain scores using VAS at rest and on movement at 1, 24, 48 and 72 hours. Patient satisfaction scores at 24 and 48 hours. Nausea

scores at 1, 24, 48 and 72 hours. Sedation scores at 1, 24, 48 and 72 hours. Time to first bowel movement, incidence of urinary retention, and incidence of respiratory depression will be recorded as well.

Secondary Research Hypotheses: ESP blocks will show improved pain control, improved patient satisfaction scores, and decreased nausea and sedation scores compared to surgeon infiltration. Statistical analysis will be performed using a standard statistical program (SAS or SPSS). All data will be summarized (means, standard deviations, standard errors, and ranges for continuous variables; frequencies and percentages for categorical variables) by group. Demographic data will be compared between the three groups using ANOVA or chi-square tests as appropriate. The primary outcome, VAS at 24 and 48 hours, will be compared between the groups using repeated measures ANOVA; the model will include fixed effects for group, time, and the group by time interaction and random effects to allow correlations between the two times and different variances for the two times. Pain and satisfaction scores and opioid usage over time will be analyzed using repeated measures ANOVA. Nausea and sedation scores will be compared between groups at each time point using Mantel-Haenszel chi-square tests for ordered categorical data. Distributions of the continuous variables will be examined, and a transformation of the data (e.g. natural logarithm) or nonparametric tests will be used as necessary. A 5% significance level will be used for all comparisons.

Based on prior studies, the coefficient of variation for the VAS score at 24 and 48 hours is estimated to be 0.70. With a sample size of 40 per group, the study will have 91% power be able to detect a 60% decrease in VAS score between any two groups, assuming two-sided tests each conducted at a 5% significance level.

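### The ESP arm is split to compare duration of action, but no time of offset is measured, so a gain lying mostly between 1 and 24 h is largely invisible to the primary outcome

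*Combined protocol and SAP*

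**What the plan says.** Section 1.0 Background explains the third arm, in which the ESP group is divided between the two formulations: "In order to compare the duration of action of both form of bupivacaine". It predicts that "LB will be superior to SB for ESP block duration of action", and says that "LB can provide analgesia coverage for up to 72 hours postoperatively when compared to normal saline". It also cites studies in which LB might not outlast standard bupivacaine (SB).

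Section 8.0 Statistical Considerations carries the idea into the primary hypothesis: "ESP with LB will provide longer pain control than ESP with SB". The outcome attached to it is fixed in time: "Primary outcome: VAS score at 24 and 48 hours". The secondary list adds "Pain scores using VAS at rest and on movement at 1, 24, 48 and 72 hours", and Section 5.0 Study Procedures confirms the schedule: "All these parameters will be measured at 1, 24, 48 and 72 hours". Opioid doses are quantified at the same four times (Sections 2.0, 5.0 and 8.0).

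The only times to an event that are collected are to first flatus or bowel movement and to discharge. The documents define no block offset, include no sensory testing or time to first opioid, and plan no time-to-event analysis. The nearest thing to a duration test is the group-by-time term in the repeated measures model for VAS at 24 and 48 h.

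**The concern.** Duration is a length of time, and the plan takes readings at four moments. A block that ended at 5 h and one that ended at 23 h look the same at the 24 h visit: both have worn off. Which gains in duration the trial can see therefore depends on whether the gain happens to cross a visit. Adding 72 h to the primary analysis would not open the 1–24 h gap.

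The gap may be wider in practice. ESP blocks are placed before surgery and opioid readings are timed from the block, so the 1 h reading may fall during the operation, whose length is not given.

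At stake is how a null LB-versus-SB result is read. It could be reported as no gain in duration when the trial did not look where the gain was.

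**Working it through.** **The plan's own power figure.** Inputs from Section 8.0: 40 per group, coefficient of variation 0.70, two-sided 5%, stated power 91%. On the log scale the SD is √ln(1 + 0.70²) = 0.6315, and the standard error of a two-group difference is 0.6315 × √(2/40) = 0.1412. A 1.6-fold ratio gives ln 1.6 / 0.1412 = 3.33, and power Φ(3.33 − 1.96) = 91.4%. So the 91% is recovered if the stated 60% is read as a 1.6-fold ratio; a literal 60% decrease gives 97.0% on the raw scale with constant SD. On either reading it is power for a VAS difference at a fixed time. No effect size is given for duration.

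**Assumptions for the duration question.** The documents give no block durations, so all of these are assumed:
- Durations are lognormal, with log-SD 0.4 or 0.8.
- Mean VAS is 2 while the block works and 5 afterwards.
- VAS SD is 2.45 (0.70 × 3.5, the midpoint of 2 and 5).
- There are 40 patients per arm and tests are two-sided at 5%.

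**VAS at 24 h.** The share still working at 24 h is p = 1 − Φ(ln(24/median)/log-SD). The expected difference is 3 × (p_LB − p_SB). Its standard error is √{[2 × 2.45² + 9 × (p_SB(1 − p_SB) + p_LB(1 − p_LB))]/40}.

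For 12 v 18 h, log-SD 0.4:
- p_SB = 1 − Φ(1.733) = 0.042 and p_LB = 1 − Φ(0.719) = 0.236.
- The difference is 0.58 and the standard error is √{[12.005 + 9 × 0.220]/40} = 0.591.
- Power is about 17%.

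| Medians, SB v LB | log-SD | Working at 24 h | Difference | SE | Power |
|---|---|---|---|---|---|
| 6 v 12 h | 0.4 | 0% v 4% | 0.12 | 0.556 | 6% |
| 6 v 12 h | 0.8 | 4% v 19% | 0.46 | 0.587 | 12% |
| 12 v 18 h | 0.4 | 4% v 24% | 0.58 | 0.591 | 17% |
| 12 v 18 h | 0.8 | 19% v 36% | 0.50 | 0.622 | 13% |
| 12 v 30 h | 0.4 | 4% v 71% | 2.01 | 0.596 | 92% |
| 12 v 30 h | 0.8 | 19% v 61% | 1.25 | 0.623 | 52% |

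Simulation agrees: 5–6% for 6 v 12 h, 15–18% for 12 v 18 h and 90–92% for 12 v 30 h at log-SD 0.4, and about 50% for 12 v 30 h at log-SD 0.8. For 12 v 18 h at log-SD 0.4, the mean of the 24 and 48 h scores has about 10% power. The group-by-time contrast has about 16%, with an assumed correlation of 0.5 between the two scores. A second simulation, with VAS multiplied by 0.4 while the block works, showed the same pattern: 8–21% at 24 h for 12 v 18 h, and 99–100% for 12 v 36 h.

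**The 24 h opioid total.** Suppose it is cumulative and opioid use runs at 2 units per hour while the block works and 5 afterwards. At the medians, 12 h of block gives 2 × 12 + 5 × 12 = 84 and 18 h gives 2 × 18 + 5 × 6 = 66. For 6 v 12 h the totals are 102 v 84. Simulated over the whole distribution (log-SD 0.4) with a between-patient CV of 0.6, power is about 35–40% in both cases. Duration and strength are not separable: a block lasting the same 12 h but with opioid use at 0.5 per hour also gives 0.5 × 12 + 5 × 12 = 66.

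**The case against.** The design does give duration a workable meaning. For an extended-release product, asking whether pain is still lower at 24 and 48 h is coarse but valid. Section 1.0 motivates LB by coverage of up to 72 h, so the gain it hopes for crosses a visit, and VAS then has good power unless durations vary widely. No passage suggests that a gain confined to the first 24 h is the expected one. All of this stands. It limits the point without removing it: the 72 h figure is against saline, and the same section cites studies in which LB did not outlast SB. The trial should not depend on the favourable answer in order to be readable.

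A reader might infer that the trial cannot answer its duration question at all. The documents do not support that, because a gain crossing 24 or 48 h is visible.

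A reader might also infer that time to first opioid dose would recover nearly all the lost power and should carry the duration claim. That would hold only if true block offset were observed. Every patient has a hydromorphone PCA (Section 5.0) and may press it for other reasons while the block still works. Take first use as the earlier of block offset and an unrelated press, counted from 4 h, with the unrelated press at a median of 3, 6 or 12 h after that (assumed). At log-SD 0.4, power is then about 8%, 22% or 54% for 12 v 18 h, and 9%, 35% or 88% for 12 v 30 h, where VAS at 24 h already has about 90%. The proxy is useful support, but can do worse than the planned outcome.

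**Conclusion.** The point holds in a limited form. The stated purpose of splitting the ESP arm is a comparison of duration, and no planned measure records when a block ends. A gain that crosses the 24 or 48 h visit will usually show as lower VAS. A gain mostly inside 1–24 h is largely invisible to the primary outcome, and the 24 h opioid total covers it only in part.

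The mismatch between purpose and measurement is plain from the text. The sizes are illustrations: they rest on assumed durations, VAS levels and opioid rates, and on the 24 h opioid figure being cumulative, which the documents do not state. The primary analysis remains valid for pain at 24 and 48 h. What needs limiting is the conclusion about duration drawn from it.

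**What to change.** Keep VAS at 24 and 48 h as the primary outcome. In Sections 5.0 and 8.0, add two supportive secondary analyses of group 1 v group 2, taken from the time-stamped PCA and medication records if these are kept (the documents do not say):

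- Opioid use in shorter intervals from block completion, for example 6–12, 12–24, 24–36, 36–48 and 48–72 h.
- Time to first opioid dose after leaving recovery, censored at 72 h or discharge, compared with a log-rank test.

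State in Section 8.0 that the VAS result supports only the conclusion that pain was, or was not shown to be, lower at 24 and 48 h, and that a null VAS result is not evidence of equal duration. Do not let first opioid use alone carry the claim of longer pain control.

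The cost is protocol wording and some record extraction, with no extra visits. The downside is that both measures are noisy proxies, and their power depends on how often patients press the PCA while the block still works.

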2.0 Rationale and Specific Aims

The specific aim of the study is to compare the difference between the ESP block and surgeon infiltration in achieving the following:

- 1. Improved postoperative pain scores
- 2. Decreased opioid requirements
- 3. Improved patient satisfaction scores
- 4. Decreased opioid side effects (Nausea, sedation, ileus, urinary retention, respiratory depression)

The primary endpoint of this study will be VAS pain score. The VAS scores will be taken with both rest and movement.

The secondary endpoint includes intravenous opioid consumption and opioid side effects (nausea, sedation, ileus, urinary retention, respiratory depression). The IV and PO opioid doses will be quantified at 1, 24, 48, and 72 hours. We will also measure postoperative nausea and sedation scores at 1, 24, 48, and 72 hours. We will measure time to first flatus, incidence of urinary retention, incidence of respiratory depression, and time to discharge.

All patients will receive a phone survey 6 months after surgery to assess for pain and quality of life.

3.0 Inclusion/Exclusion Criteria

Inclusion criteria:

- Pt undergoing VATS including but not limited to wedge or lobectomy at Indiana University Hospital,
- ASA 1,2,3 or 4
- Age 18 or older, male or female
- Desires regional anesthesia for postoperative pain control

Exclusion criteria:

- Any contraindication for Erector Spinae Plane block
- History of substance abuse in the past 6 months which would include heroin, marijuana or any other illegal street drugs
- Patient staying intubated after surgery
- Patient (home dose) taking more than 30mg PO morphine equivalent per day
- Known allergy or other contraindications to the study medications, which include dilaudid and bupivacaine.

- Pts. scheduled for a pleurodesis, decortication or esophagectomy at Indiana University Hospital
- BMI greater than 40.0.

4.0 Enrollment/Randomization

All VATS cases scheduled by thoracic surgeons at IU Health University Hospital will be identified. The subjects will be contacted initially face-to-face by either [name] or [name] in their clinics prior to their scheduled surgery date. They will be given a copy of the consent and authorization form explaining this study. The subjects will again be contacted face to face in POCU on the day of surgery and the study will be explained in detail and all questions will be answered. If participation is agreed, written consent will be taken and a signed copy of both the authorization and consent will be given to the participant.

A total of 120 subjects will be randomized by the computer program Research Randomizer into three groups (40 per group): The primary investigator will inform the anesthesiologist who will be doing the block as to what group the patients are randomized to. The research staff completing the patients assessments will be the only person blinded to the randomization.

- 1. Ultrasound guided LB Erector Spinae Plane Block with 20ml of Exparel® and 10ml 0.25% bupivacaine
- 2. Ultrasound guided SB Erector Spinae Plane Block with 30ml 0.5% bupivacaine
- 3. Surgeon Infiltration under video guidance with 20ml of Exparel® and 10ml of 0.25% bupivacaine

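### As written, Section 4 provides for no patient blinding, although LB-ESP versus SB-ESP, part of the primary hypothesis on a self-rated VAS, could be patient-blinded at little cost

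*Combined protocol and SAP*

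**What the plan says.** Section 4.0 randomises 120 patients equally to ESP block with LB, ESP block with SB, or surgeon infiltration with LB. On blinding it says: "The research staff completing the patients assessments will be the only person blinded to the randomization". The only transfer of allocation it describes is to the person placing the block: "The primary investigator will inform the anesthesiologist who will be doing the block as to what group the patients are randomized to".

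Section 8.0 defines "Primary outcome: VAS score at 24 and 48 hours" and includes in the primary research hypothesis that "ESP with LB will provide longer pain control than ESP with SB". Its secondary outcomes include "Patient satisfaction scores at 24 and 48 hours".

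Section 5.0 describes one ESP procedure for both ESP groups. On timing: "All the erector spinae plane blocks will be placed preoperatively after sedation, before intubation and prior to surgery". On site: "ultrasound probe is used to visualize the ES musculature about 3 cm laterally from the T5 spinous process". Infiltration is done by the surgeon during the operation, under thoracoscopic view. Section 5.0 also gives all patients a hydromorphone PCA and a 6-month telephone call using the Brief Pain Inventory. It assigns the VAS measurement to the investigator.

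**The concern.** A VAS pain score is the patient's own report. A blinded assessor can hand over the scale and record the mark without influencing it, but cannot remove an expectation that the patient already holds. A patient who knows that he or she received the longer-acting formulation may rate pain accordingly, and the sponsor's hypothesis favours that same formulation. Satisfaction scores, PCA use and the 6-month questionnaire are open to the same influence, because the patient reports or drives each of them.

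At stake is the interpretation of LB versus SB. A difference could not be cleanly attributed to the drug, although the design would allow patients to be kept unaware of it.

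**Working it through.** The plan gives no figure on blinding to reproduce. Its 91% power statement depends on the group size, the coefficient of variation, the difference and the significance level. The change proposed here touches none of these.

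**1. Who is blinded.** Section 4.0 limits blinding to the assessing staff by using the word *only*. Sections 5.0 to 8.0 contain nothing that extends it to patients. Patient non-blinding is therefore the literal rule of the plan and not merely a silence.

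**2. Can the two ESP arms be told apart by the patient?**

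| Feature | LB-ESP | SB-ESP | Infiltration |
|---|---|---|---|
| Technique | Ultrasound-guided ESP block | Ultrasound-guided ESP block | Surgeon, under video guidance |
| Timing | Before surgery, after sedation | Before surgery, after sedation | During surgery |
| Site | Beside T5 | Beside T5 | Intercostal spaces, typically T4 to T8 |
| Volume | 20 + 10 = 30 ml | 30 ml | 20 + 10 = 30 ml prepared |

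The SB arm is specified as "Ultrasound guided SB Erector Spinae Plane Block with 30ml 0.5% bupivacaine". Between the two ESP arms only the drug content differs, so nothing in the described procedure need reveal the formulation to the patient. Infiltration differs from both in timing and site, so a patient may notice whether a block was placed before surgery.

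**3. How much of the trial this reaches.**
- Patients: 40 + 40 = 80 of 120; 80/120 = 66.7%.
- Pairwise comparisons: three arms give 3. Only LB-ESP versus SB-ESP shares route, site and timing, so 1 of 3.
- Planned patient assessment times: 1, 24, 48 and 72 hours and 6 months, so 5. Withholding to 72 hours covers 4 of 5, including both primary times and every Section 8.0 outcome that has a fixed time. Withholding to the 6-month call covers 5 of 5.

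**4. Illustration only, with an assumed bias.** Suppose LB and SB are truly equal, and knowing the formulation shifts mean VAS at one time point by a fraction b of the mean. Take the plan's coefficient of variation of 0.70 as SD/mean, 40 per arm, and a two-sided 5% t-test with 78 degrees of freedom. The noncentrality is (b/0.70) × √(40/2).

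| Assumed b | Noncentrality | Chance of a significant difference |
|---|---|---|
| 0 | 0 | 5.0% |
| 5% | 0.32 | 6.1% |
| 10% | 0.64 | 9.7% |
| 15% | 0.96 | 15.7% |
| 20% | 1.28 | 24.3% |

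The values of b have no source in the documents. The table shows only that such a bias would matter if it were present.

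**The case against.** The strongest objection is that the harm is conditional. Bias requires patients to know their formulation. A reader might infer from Section 4.0 that patients are told their group, but the documents do not support that. The only disclosure described goes to the anesthesiologist, the ESP block follows sedation, and the consent pages are not available. The sentence could also be a loose statement about study staff. This stands as a limit: actual disclosure is not shown. It does not remove the point, because the text as written gives no basis for calling LB versus SB patient-blinded, and gives nobody a duty to keep the formulation from patients.

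The benefit is also narrow. The specific aims in Section 2.0 and the secondary hypotheses in Section 8.0 concern ESP versus infiltration, and that contrast gains nothing from patient blinding of the formulation. This stands too. Nevertheless, LB versus SB is in the primary hypothesis.

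Third, the 6-month questionnaire is not among the outcomes listed in Section 8.0, so concealment beyond 72 hours protects no outcome listed there with a fixed time. This is correct. It is why 72 hours is the minimum below and the 6-month call only a preference.

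Finally, blinding may leak, so labelling the comparison as patient-blinded in advance could prove untrue. This stands as well, and is met by recording disclosures and describing the blinding as planned.

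**Conclusion.** The point holds in a limited form. The plan as written does not provide for patient blinding, and for one comparison in the primary hypothesis this can be put right cheaply. The reach is 80 of 120 patients and 1 of 3 pairwise comparisons. The conclusion rests on three things: VAS is the patient's own rating, which the term implies although Section 5.0 names the investigator as measuring it; the ESP procedure is the same in both arms apart from the drug; and *only* in Section 4.0 means what it says.

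Two further inferences would go too far. The documents do not show that an LB versus SB result would be biased, or by how much. Nor do they suggest that withholding allocation could make ESP versus infiltration reliably patient-blinded. This is a worthwhile improvement to the design, not a reason to regard the trial as invalid.

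**What to change.** **Section 4.0.** Replace the sentence on blinding with: *Patients in the two ESP groups will not be told which bupivacaine formulation they received, at least until the 72-hour assessment and preferably until the 6-month call is complete, unless needed for safety; any disclosure will be recorded. Staff who carry out the assessments are also blinded. Treating teams will be instructed not to disclose the formulation to patients or assessors.* Align the consent wording with this.

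**Section 8.0.** Describe LB versus SB as planned to be patient- and assessor-blinded, with the number of recorded disclosures reported. Describe ESP versus infiltration as assessor-blinded only.

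**Section 5.0, a separate clarification.** Section 4.0 has the primary investigator holding the allocation, while Section 5.0 has the investigator measuring VAS. Reconcile the two by naming the blinded research staff as the VAS assessors.

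**Cost.** Protocol and consent wording, an instruction to the treating teams, and a simple record of disclosures. Sample size, procedures, staffing and visits do not change, and no sham procedure is involved. The downside is that treating staff must withhold the formulation. They include the acute pain resident, who according to Section 6.0 is not listed on the study. Some patients may still learn or infer what they received.
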